5.3.5 Treatment Compliance

The treatment in this study includes a single dose injection administered by the study Investigator. Measurement of treatment compliance is not applicable to this study.

5.3.6 Restrictions

Subjects will be instructed to remain seated for approximately 30 minutes following the AXT107 IVT. Subjects should be advised that they should avoid vigorous exercise such as jumping jacks, aerobics, yoga, lifting weights, etc. within a month after the AXT107 IVT.

5.4 Study Drug Management and Handling

5.4.1 Investigational Drug

Study medication will be tested in 3 concentrations in this study; the 0.1 mg solution is considered the "low dose", the 0.25 mg solution is considered the "mid dose", and the 0.5 mg

solution is considered the “high dose”. Syringes and needles will be utilized to administer the study medication (See the MOP and Pharmacy Manual for administration instructions).

5.4.2 Study Drug Packaging and Labeling

AXT107 will be provided as a lyophilized powder in a vial. The study drug will be reconstituted, as described in the Pharmacy Manual, for injection to provide the appropriate dose. The label will include the name of the study drug, the protocol number, kit number, and storage conditions. The Carton will include a statement that indicates the product is for investigational use only.

5.4.3 Study Drug Storage

AXT107 is to be stored at 2-8°C, in a securely locked area with access given only to appropriate study personnel.

5.4.4 Additional Clinical Supplies

Urine pregnancy test kits and clinical laboratory supplies for obtaining blood and urine specimens will be provided by the central laboratory.

5.4.5 Study Drug Accountability

It is the responsibility of the Principal Investigator (or designee) to ensure the receipt, accountability, proper storage, and dispensing of study drug. Inventory procedures should be in place and conducted upon receipt of study drug and supplemental supplies (e.g., syringes), and any discrepancy is to be communicated to the Sponsor immediately upon awareness by the Principal Investigator. The clinical supplies shipment form must be completed and a copy must be returned to the Sponsor as directed, while the original record is retained in the clinical trial files. A current record of the inventory, storage conditions, and dispensing must be kept by the investigative site staff, and will be provided to the Sponsor representatives (Study monitor) when necessary for the purpose of accounting for all clinical supplies. Any discrepancy and/or deficiency must be recorded with provided explanation.

5.4.6 Return of Unused Supplies

All unused supplies are to be returned to the Sponsor upon completion of the study. It is the responsibility of the Principal Investigator to ensure the proper packaging and shipment of clinical supplies when returning to the Sponsor. The site's standard practice will be followed for the disposal of used study drug supplies.

5.5 Assessment of Safety

5.5.1 Definitions and classification of Adverse Events

An adverse event (AE) is considered as any untoward medical occurrence associated with the use of a drug product in humans, whether or not considered drug related. An adverse event (also referred to as an adverse experience) can be any unfavorable and unintended sign (e.g., an abnormal laboratory finding), symptom, or disease temporally associated with the use of a drug, and does not imply any judgment about causality. An adverse event can arise with any use of the drug (e.g., off-label use, use in combination with another drug) and with any route of administration, formulation, or dose, including an overdose.

Life-threatening adverse event or life-threatening suspected adverse reaction: An adverse event or suspected adverse reaction is considered "life-threatening" if, in the view of either the Investigator or Sponsor, its occurrence places the patient or subject at immediate risk of death. It does not include an adverse event or suspected adverse reaction that, had it occurred in a more severe form, might have caused death.

Serious adverse event or serious suspected adverse reaction: An adverse event or suspected adverse reaction is considered "serious" if, in the view of either the Investigator or sponsor, it results in any of the following outcomes:

- Death
- a life-threatening adverse event
- inpatient hospitalization or prolongation of existing hospitalization
- a persistent or significant incapacity or substantial disruption of the ability to conduct normal life functions
- a congenital anomaly/birth defect

Important medical events that may not result in death, be life-threatening, or require hospitalization may be considered serious when, based upon appropriate medical judgment, they may jeopardize the patient or subject and may require medical or surgical intervention to prevent one of the outcomes listed in this definition. Examples of such medical events include allergic bronchospasm requiring intensive treatment in an emergency room or at home, blood dyscrasias or convulsions that do not result in inpatient hospitalization, or the development of drug dependency or drug abuse.

Suspected adverse reaction: Any adverse event for which there is a reasonable possibility that the drug caused the adverse event. For the purposes of IND safety reporting, "reasonable possibility" means there is evidence to suggest a causal relationship between the drug and the adverse event. Suspected adverse reaction implies a lesser degree of certainty about causality than adverse reaction, which means any adverse event caused by a drug.

Unexpected adverse event or unexpected suspected adverse reaction: An adverse event or suspected adverse reaction is considered "unexpected" if it is not listed in the Investigator brochure or is not listed at the specificity or severity that has been observed; or, if an Investigator brochure is not required or available, is not consistent with the risk information described in the general investigational plan or elsewhere in the current application, as amended. For example, under this definition, hepatic necrosis would be unexpected (by virtue of greater severity) if the Investigator brochure referred only to elevated hepatic enzymes or hepatitis. Similarly, cerebral thromboembolism and cerebral vasculitis would be unexpected (by virtue of greater specificity) if the Investigator brochure listed only cerebral vascular accidents. "Unexpected," as used in this definition, also refers to adverse events or suspected adverse reactions that are mentioned in the Investigator brochure as occurring with a class of drugs or as anticipated from the pharmacological properties of the drug, but are not specifically mentioned as occurring with the particular drug under investigation.

5.5.2 Collection and Assessment of Adverse Events

In this study, AEs are to be collected from the time of informed consent. Therefore, any undesirable medical condition occurring at any time, including Baseline or pre-treatment period

(even if no study drug has been administered), must be evaluated for an AE. Any clinically significant change from baseline in a subject's condition or pre-existing condition must be evaluated as an AE, unless the change is determined to be a continuation of a pre-existing condition that is documented in the subject's medical history. However, a clinically significant worsening in severity, intensity, or frequency of a pre-existing condition may indicate an AE.

All conditions that lead to hospitalizations, defined as an overnight hospital stay, are to be considered as SAEs. Elective surgical procedures scheduled or planned prior to study entry that do not require overnight hospital stay, and the underlying diagnosis for which surgery is to be performed is captured in the medical history as a pre-existing condition are not considered AEs. The surgical procedure should still be documented in the subject records with an explanation of circumstances.

Lack of efficacy of AXT107 for the condition being investigated is not considered an AE unless a clinically significant change is assessed by the Principal Investigator.

Adverse events in this study will be collected by way of seeking information (direct questioning and physical examination) by the Investigator at each subject contact, or upon information that is provided voluntarily by the subject, and are to be followed to resolution, or until the condition is determined to be irreversible, chronic, or stable, for up to 30 days after the subject's exit from the study. Unresolved AEs beyond 30 days of the subject's exit from the study should be evaluated on a case-by-case basis, depending upon the condition and based on the clinical judgement of the Investigator or at the direction of the Sponsor.

Adverse events will be assessed by the Investigator for seriousness (see CFR 21 part 312 criteria in Section 6.5.1) and severity according to the following criteria:

Mild: No interference with the subject's daily activities; no medical intervention/therapy required

Moderate: Possible interference with the subject's daily activities; no or minimal medical intervention/therapy required

Severe: Considerable interference with the subject's daily activities; medical intervention/therapy required

The Investigator must also make a determination of relatedness to the study drug (related or not related), based on the Investigator's clinical judgment, facts (product information or Investigator's Brochure), evidence, and scientific rationales as to whether there is a causal relationship between the AE and AXT107.

- An AE must be reported as **Related** to AXT107 if there is a reasonable possibility that the experience may have been caused by AXT107, and the AE cannot be readily explained by the subject's clinical state, concurrent illness, or concomitant therapies.
- An AE may be considered as **Not Related** to AXT107 if evidence that the AE has an etiology other than the AXT107 (e.g., pre-existing medical condition, underlying disease, concurrent illness, or concomitant medication); and/or the AE has no plausible temporal relationship to administration of the AXT107 (e.g., newly diagnosed condition after administration of AXT107).

The Investigator will be required to assess the outcome of the AE as one of the following:

- Resolved
- Resolved with sequelae
- Resolving
- Not Resolved
- Fatal
- Unknown

An event that is assessed as resolved with sequelae or resolving indicates that the subject has stabilized to a level acceptable to the Investigator and has concurrence by the Sponsor.

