5.1.4 Criteria for Termination of the Study (Stopping Rules)

The DMC will conduct ongoing reviews of collected safety data to determine the need for early termination of the study. Stopping rules will be incorporated if any of the following events are identified:

- Decrease in Early Treatment Diabetic Retinopathy Study (ETDRS) best corrected visual acuity (BCVA) of ≥ 15 letters (3-line decrease) unrelated to the natural progression of the disease and determined by the Investigator to be related to the study drug in ≥ 2 subjects
- Intraocular inflammation (anterior or posterior) grade +2 or more in ≥ 2 subjects (using SUN Grading Working Group and Nussenblatt et al grading)
- Increase in intraocular pressure (IOP) to ≥ 30 mmHg for more than 24 hours post-injection in ≥ 2 subjects despite IOP lowering medication treatment
- Any other serious ocular or systemic adverse event (AE) that, in the opinion of the Investigator, is related to the study drug in ≥ 1 subject

Upon DMC's recommendation for study termination, further enrollment of study subjects in the study will be discontinued. Subject withdrawal procedures must be followed for all active subjects to ensure the safety of the subjects at the conclusion of the study.

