6.3 Statistical Methods

Age, sex, race, ethnicity, and baseline assessments will be summarized and listed by dose level. Medical history, history of ocular surgery and procedures, and concomitant medication will also be summarized and listed.

Changes from baseline in BCVA and retinal thickness (CST) will be summarized by dose level using continuous summary statistics. BCVA change will be summarized using categorical summaries as well, including frequency counts and percentages improving at least 5, 10, and 15 letters.

Verbatim descriptions of AEs will be mapped to MedDRA thesaurus terms and be presented in a data listing. Treatment emergent AEs, those that occur after the first dose of study medication, will be summarized by dose level using frequency and percent for each system organ class (SOC) and preferred term (PT) within each SOC. Summaries will be presented separately for ocular and non-ocular AEs. TEAEs will be summarized by severity and study drug relatedness.

BCVA will be summarized at each time point using both continuous summaries (ETDRS letter score), including change from Baseline (Day 0), and categorical summaries, including change from Baseline (Day 0) on an ETDRS chart in the number of lines.

IOP will be summarized at each time point using both continuous summaries, including change from Baseline (Day 0), and categorical summaries for pre-stated categories of change in IOP.

Slit lamp biomicroscopy and ophthalmoscopy measures will be summarized at each measured time point using categorical summary statistics.

FA will be summarized by visit.

DRSS will be summarized by visit and change from Baseline (Day 0) to each visit.

Vital signs will be summarized at each visit and for change from Baseline (Day 0) to each visit using continuous summary statistics by treatment group and visit.

Clinical laboratory results will be summarized using both continuous summaries, including change from Baseline (Day 0), and discrete summaries, including frequency and percent of subjects with an abnormal value and shift tables from Baseline (Day 0). Additionally, laboratory data will be presented in data listings.

Exploratory analyses will be performed to summarize the results obtained from the Notal Vision Home OCT device and home M&S® Technology visual acuity measurement.

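### The only example of implausible timing in the Not Related definition is a condition newly diagnosed after injection, which contradicts the test it illustrates and can lower the Related counts and two relatedness-dependent stopping criteria

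*Combined protocol and SAP*

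**What the plan says.** Section 5.5.2 sets a two-level scale: "The Investigator must also make a determination of relatedness to the study drug (related or not related". Two bullets then define the levels.

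- **Related** is mandatory. An event must be reported as Related "if there is a reasonable possibility that the experience may have been caused by AXT107", provided the subject's clinical state, concurrent illness or other therapy does not readily explain it.
- **Not Related** is permissive. An event may be so considered on either of two limbs, joined by and/or. The first is evidence of another cause, with a pre-existing condition among its examples. The second is that "the AE has no plausible temporal relationship to administration of the AXT107 (e.g., newly diagnosed condition after administration of AXT107" applies. No other example is given for the second limb.

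Section 6.3 defines treatment-emergent events as "those that occur after the first dose of study medication" and plans that "TEAEs will be summarized by severity and study drug relatedness".

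Section 5.1.4 lists four stopping criteria, two of which use the Investigator's causality call. The vision-loss criterion (15 letters or more) counts loss "determined by the Investigator to be related to the study drug in ≥ 2 subjects". The last criterion counts any other serious event that, "in the opinion of the Investigator, is related to the study drug in ≥ 1 subject". The inflammation and intraocular pressure criteria do not refer to relatedness.

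**The concern.** An example in a coding rule tells the Investigator what the rule means in practice. Here it describes an event that first comes to light after the injection, which is the ordinary situation in which a drug effect has to be considered. Because of the and/or, the timing limb is enough by itself, and no alternative cause need be identified.

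The stakes come from the design. Safety and tolerability are the primary objective (Section 4). Section 3.4 states that this is the first human study and that the risks are not well understood. There is no control arm or masking, and the two-level scale has no intermediate category for doubtful cases. A causality call that leans toward Not Related would not be exposed by comparison with another arm.

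**Working it through.** The plan states no event rate, error rate or power, so there is no figure to reproduce. The check is mainly a comparison of texts.

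**Step 1: the example against its own test.** The test is that timing makes a link implausible. The example is a diagnosis after dosing. Such timing does not prove causation, but it does not make causation implausible either. Nothing in the sentence limits the example to conditions that began before the injection.

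**Step 2: the example against Section 6.3.** Treatment-emergent events are "those that occur after the first dose of study medication". Diagnosis and onset are not the same thing, so the two sets are not identical, but they overlap heavily: a new condition that begins and is diagnosed after Day 0 belongs to both.

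**Step 3: the example against the Related bullet.** Take a new condition found after injection, with no ready alternative explanation and a reasonable possibility of drug cause. The first bullet says it must be Related. The second, read through its example, says it may be Not Related. Section 5.5.2 does not say which governs.

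**Step 4: does late timing rescue the example?** Section 3.3 reports ocular exposure in rabbits for up to 12 months, and Section 5.5.4.4 provides for drug still visible at Week 48. On the plan's own information, even a late diagnosis can be temporally plausible.

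**Step 5: where the call is used.** It enters the relatedness summary in Section 6.3 and 2 of the 4 stopping criteria in Section 5.1.4, with thresholds of 2 subjects and 1 subject.

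**Step 6: illustration of size.** Let n = 18 (3 doses × 6, Section 6.4). Let p be the true chance per subject of a qualifying drug-caused event and m the share of these coded Not Related. Both p and m are assumptions. With q = p(1 − m), subjects independent and the same p at every dose:

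- at least 1 subject: 1 − (1 − q)^n
- at least 2 subjects: 1 − (1 − q)^n − nq(1 − q)^(n−1)

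For p = 10% and m = 0, the first is 1 − 0.9^18 = 85.0%. With m = 0.5, q = 0.05 and it is 1 − 0.95^18 = 60.3%.

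| Criterion | p | m = 0 | m = 0.25 | m = 0.5 |
|---|---|---|---|---|
| Other serious event, at least 1 | 5% | 60.3% | 49.7% | 36.6% |
| | 10% | 85.0% | 75.4% | 60.3% |
| | 20% | 98.2% | 94.6% | 85.0% |
| Vision loss, at least 2 | 5% | 22.6% | 14.5% | 7.3% |
| | 10% | 55.0% | 39.6% | 22.6% |
| | 20% | 90.1% | 77.6% | 55.0% |

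In a first cohort of 3 at p = 10%, the serious-event criterion goes from 1 − 0.9^3 = 27.1% to 1 − 0.95^3 = 14.3% when m = 0.5. These are chances that a criterion is met. They are not chances that the study stops, since the synopsis leaves that to the DMC.

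**The case against.** The case for leaving the text alone has several sound parts.

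- **Tables.** A reader might infer that affected events vanish from the relatedness tables. They do not. A Not Related event stays in the system organ class and preferred term counts, the severity and relatedness summaries, and the listing. Only the Related count falls.
- **Force of the example.** A reader might infer that every diagnosis after Day 0 has to be coded Not Related. The text does not say that. The example illustrates a test that still calls for clinical judgment, and the clause says *may* while the Related clause says *must*. An Investigator who reads both carefully can reach the right code.
- **Oversight.** The DMC reviews collected safety data on an ongoing basis (Section 5.1.4), escalation depends on an acceptable safety profile without a relatedness filter (Section 5.1.3), and serious events are reported within 24 hours whatever their causality (Section 5.5.3.1). It would be wrong to infer that such events are hidden.
- **Vision loss.** A measured loss of letters is less naturally called a new diagnosis, so the example bears more directly on the serious-event criterion. It reaches the vision-loss criterion when the loss is put down to a newly found condition.
- **Intended meaning.** The drafters may have had in mind a long-standing disease first detected after injection.

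The first four points limit the consequence and are accepted. The last does not repair the text: that meaning is not written, and the first limb already covers pre-existing conditions. None of the safeguards changes the causality code on which the two criteria and the Related counts depend.

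**Conclusion.** The example contradicts the criterion it is meant to illustrate and should not stand. It permits, but does not require, a new post-injection event to be coded Not Related, and it can collide with the mandatory Related bullet with no stated order of precedence. The consequence is bounded: such events leave the Related counts and do not count toward two of the four stopping criteria, while remaining in the safety outputs and open to DMC review.

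The documents do not allow the size to be estimated. What follows from them directly is that the thresholds are 1 and 2 subjects, so one or two coding decisions can determine whether a criterion is met. The percentages above rest on assumed event rates and miscoding shares and only show the direction and possible scale. The documents do not show that any event has been miscoded. They also do not support the inference that the stopping rules are disabled.

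**What to change.** In Section 5.5.2:

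1. Delete the example, or replace it with one that shows implausible timing, such as onset or clear evidence of the condition before the injection. Because the pre-existing-condition limb largely covers that case, deletion may be the cleaner choice.
2. State that onset or diagnosis after injection does not by itself support Not Related.
3. State that the mandatory Related bullet prevails where both bullets could apply.
4. Check any events already coded Not Related on timing alone, and query the sites about them.

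The stopping criteria, sample size and planned summaries need no change. The cost is a short wording amendment, notice to sites and a brief query round. Some events may move from Not Related to Related, which would raise the Related counts and could bear on the two criteria that use them.

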5.5.3 Reporting of Adverse Events

All AEs reported after the subjects has provided written informed consent and within 30 days following the last visit will be recorded in the subject's medical records and the appropriate CRF.

Recognized medical terms should be used when recording the AE, avoiding colloquialisms and/or abbreviations when possible. Separate AEs should be reported for events that are observed simultaneously but are deemed to be unrelated based on the clinical judgement of the Investigator. If a diagnosis cannot be established, the prominent sign, symptom, or finding should be documented as the AE description. Intermittent events should be reported with the date of the first episode as the onset date, and with maximum severity as observed among the collective episodes. Intermittent hospitalizations as a result of a primary event should be documented with the primary event and not as separate events.

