- BCVA (Proportion improving ≥ 5 , ≥ 10 , and ≥ 15 letters from Baseline (Day 0))

Statistical Methods:

Sample Size Determination:

Approximately 18 subjects will be enrolled, with 6 subjects in each dose. The final number of subjects enrolled may be adjusted based on the presence of dose limiting toxicities. This sample size is not planned based on statistical considerations.

Analyses:

Age, sex, race, ethnicity, and baseline assessments will be summarized and listed by dose level. Medical history, history of ocular surgery and procedures, and concomitant medication will also be summarized and listed.

Changes from baseline in BCVA (ETDRS letter score) and retinal thickness (CST) will be summarized by dose level using continuous summary statistics. BCVA change will be summarized using categorical summaries as well, including frequency counts and percentages improving at least 5, 10, and 15 letters.

Verbatim descriptions of AEs will be mapped to MedDRA thesaurus terms and be presented in a data listing. Treatment emergent AEs that occur after the first dose of study medication will be summarized by dose level using frequency and percent for each system organ class (SOC) and preferred term (PT) within each SOC. Summaries will be presented separately for ocular and non-ocular AEs. All TEAEs will be summarized by severity and study drug relatedness.

BCVA will be summarized at each time point using both continuous summaries (ETDRS letter score), including change from Baseline (Day 0), and categorical summaries, including change from Baseline (Day 0) on an ETDRS chart in the number of lines.

IOP will be summarized at each time point using both continuous summaries, including change from Baseline (Day 0), and categorical summaries for pre-stated categories of change in IOP.

Slit lamp biomicroscopy and ophthalmoscopy measures will be summarized at each measured time point using categorical summary statistics.

FA will be summarized by visit.

DRSS will be summarized at each measured visit and change from Baseline (Day 0) to each measured visit.

Vital signs will be summarized at each visit and for change from Baseline (Day 0) to each visit using continuous summary statistics by treatment group and visit.

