² Required for all female subjects of childbearing potential. Urine pregnancy tests will be performed unless local regulations/IRBs require a serum pregnancy test.

³ Additional blood samples will be obtained during clinical laboratory collection at the Screening, Week 4, Week 12, and Week 48 visits for ADA assay.

⁴ AEs reported after screening and before randomization will be reported as pre-injection AEs.

⁵ Procedure to be performed at selected sites only.

⁶ At Week 44 only.

[figure not shown]
[figure not shown]
⁷ AXT107 visibility will be assessed via fundus exam for all subjects. Optos will be used at selected sites to evaluate AXT107 visibility at Baseline (after IVT), Week 8, and Week 36.

⁸ Stereoscopic 7-field or 4-widefield color fundus photography will be taken.

⁹ IOP measurement must be performed prior to and after the AXT107 injection at Visit 1/Baseline. After injection, IOP will be measured 30±10 minutes. If IOP >30mmHg, repeat IOP measurement at 60±10 minutes post-injection. Fundus exam will be performed before and after injection at the Baseline visit.

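### The TEAE definition has no worsening clause and intermittent AEs take their first-episode date, so an intermittent event first seen in screening can be left out of the by-dose TEAE tables even if it recurs or worsens after injection

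*Combined protocol and SAP*

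**What the plan says.** Four parts of the combined protocol and SAP bear on this.

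- **Collection (Section 5.5.2).** "AEs are to be collected from the time of informed consent", so events in the screening window (Day -14 to Day -1) are recorded as AEs.
- **Recording (Section 5.5.3).** "Intermittent events should be reported with the date of the first episode as the onset date, and with maximum severity". The result is one record with the earliest date and the worst grade of any episode. The term intermittent is not defined.
- **Analysis (Section 6.3).** "Treatment emergent AEs, those that occur after the first dose of study medication, will be summarized by dose level". Severity and relatedness summaries are also restricted to TEAEs. The Synopsis has the same rule: "Treatment emergent AEs that occur after the first dose of study medication will be summarized by dose level". Neither place mentions an event that began before dosing and then worsened or came back.
- **Class of earlier events (Appendix I, Table I-1, footnote 4).** "AEs reported after screening and before randomization will be reported as pre-injection AEs".

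Section 5.5.2 also says "Any clinically significant change from baseline in a subject's condition or pre-existing condition must be evaluated as an AE", with an exception for continuation of a condition documented in the medical history, and that "a clinically significant worsening in severity, intensity, or frequency of a pre-existing condition may indicate an AE".

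**The concern.** Each rule is workable alone. Together they can move a post-injection episode to the wrong side of the injection. The recording rule assigns the whole intermittent event to its first date. The analysis rule then asks only whether the event came after dosing. If the first episode fell in screening, a worse episode after injection can be classed as pre-injection and be absent from the by-dose, severity and relatedness tables.

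Safety and tolerability are the primary objective, this is the first use in humans, and each dose level is planned at 6 subjects. A single missing event can therefore turn a non-zero row into an empty one.

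**Working it through.** **No planned figure to reproduce.** Section 6.4 says the sample size has no statistical basis and Section 6.2 defines no hypotheses. The check traces the rules through example events and then sizes one lost event.

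**Step 1: trace the rules.** Under Section 5.5.3, recorded onset is the minimum of the episode dates and recorded severity is the maximum of the episode grades. Assume that TEAE status is derived from recorded onset, which the plan does not state. The example dates are illustrative, and each repeated event is assumed to be handled as intermittent.

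| Episodes | Recorded onset | TEAE under present rules | TEAE if post-injection episodes count |
|---|---|---|---|
| Single event, Day 10 | Day 10 | Yes | Yes |
| Mild on Day -7, severe on Day 30 | Day -7, graded severe | No | Yes |
| Day 5, recurrence on Day 300 | Day 5 | Yes | Yes |

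Only the second pattern leaves the TEAE tables. The third stays in and loses only the date of its recurrence (300 - 5 = 295 days).

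**Step 2: look for another rule that prevents this.**
- Section 5.5.2 says when a change must be evaluated as an AE and that worsening may be one. It does not say that worsening opens a new record or takes a new onset date.
- Section 6.5 imputes missing or partial AE dates. A complete Day -7 date is untouched.
- Footnote 4 sends early events to the pre-injection class. Its cut-off is randomization, which Section 5.1.2 says is not used, and it goes by when the AE was reported, not when it began.

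**Step 3: ask whether the analysis could repair it.** The combined record holds one onset date and one maximum grade. From those two fields a programmer cannot tell which episode was severe, so worsening after injection cannot be recovered from them at the analysis stage.

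**Step 4: size one lost event.** Inputs are 6 subjects per dose and about 18 in all (Section 6.4). Assume each subject counts once per table row and the affected subject has no other event in that row. Intervals are exact two-sided 95% (Clopper-Pearson).

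| | Event counted | Event left out |
|---|---|---|
| One dose level | 1/6 = 16.7% (0.4 to 64.1%) | 0/6 = 0% (0 to 45.9%) |
| All doses | 1/18 = 5.6% (0.1 to 27.3%) | 0/18 = 0% (0 to 18.5%) |

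The documents give no frequency for such events, so this is the effect of one case, not an expected loss.

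**The case against.** The strongest reply is that the first-episode rule covers only intermittent events. A screening event that simply worsens falls under Section 5.5.2, and nothing there requires it to be merged into the screening record. Section 6.3 also speaks of events that occur after the dose, not of recorded onset, and a severe episode on Day 30 does occur after the dose. Both points stand. They are why the conclusion is that an event can be left out, not that it must be. They do not close the gap, because onset is the only date rule given for repeated episodes and the plan does not say how TEAE status is derived.

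Eligibility narrows the pool further. Exclusion 6 names vitreous hemorrhage and exclusion 7 covers ongoing clinically significant inflammation. Table I-1 rechecks eligibility at Baseline. Milder events such as eye pain are still possible.

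A reader might draw three stronger conclusions that the documents do not support.

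- *The event vanishes from the safety output.* It does not. Section 6.3 puts AEs generally in a listing and summarizes BCVA, IOP, slit lamp and ophthalmoscopy findings by time point.
- *Late toxicity is hidden.* An intermittent event that began after injection is still a TEAE at its maximum severity. Section 6.3 plans no AE table by period or time to onset, so no planned AE table changes.
- *Stopping decisions depend on the TEAE definition.* Section 5.1.4 bases them on collected safety data and does not refer to TEAE status.

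**Conclusion.** The point holds in a limited form. For an intermittent event first seen between consent and injection, the recording rule and the TEAE definition can together remove a post-injection recurrence or worsening from the by-dose, severity and relatedness tables. Section 5.5.2 leaves open whether a new record prevents this.

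One affected subject is worth 16.7 percentage points in a dose-level row. This rests on three assumptions: the site treats the event as intermittent, TEAE status follows recorded onset, and the subject has no other event in that row. The exposure is confined to first episodes in a window of up to 14 days. The case is likely to be uncommon, but the wording bears on the primary objective and should be corrected.

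**What to change.** 1. **Section 6.3 and the Synopsis.** Define a TEAE as an AE that starts, or worsens in severity or frequency, on or after the AXT107 injection.
2. **Section 5.5.3.** Apply the intermittent-event rule only to episodes on the same side of the injection. The first post-injection episode of an event that began before injection opens a new record with its own onset date and severity. This is needed alongside the first change, because a single combined record does not hold the information from which worsening could be derived.
3. **Table I-1, footnote 4.** Classify pre-injection AEs by onset relative to the injection. Replacing the reference to randomization is clerical but belongs in the same edit.

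A separate record for every resolved and recurring event after injection is a data-collection convention and is not needed to close this gap.

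The cost is protocol, SAP and CRF-completion wording, a few more AE records, and TEAE counts that may be slightly higher.
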